Upon study enrollment, we will record relevant variables for the purposes of comparisons between patients, including gestational age, date and time of birth, gender, weight and length, date of admission, known medical problems, current medication list. Markers of severity of illness will include the number of organ failures, number and dosing of inotropic medications, and any positive cultures.

Adverse events

Although this is a prospective, observational study which do not anticipate will alter our standard practices, we will monitor vigilantly for complications associated with the standard therapies used in these patients for differences in study patients. Namely, we will monitor for endotracheal tube complications (e.g. ventilator associated pneumonia, accidental extubation) and for central venous line complications (e.g. catheter associated bloodstream infections).

Safety end points

Because this is a prospective observational study and is not expected to directly impact patient care, we will not have stopping rules for an individual patient per se, except if informed consent is withdrawn by a parent or team member.

Parameters for discontinuation of the research

All components of this study have been tested and validated in the critically ill newborn population. As such, we do not anticipate any technical problems with the observations proposed in this study. However, the research will be discontinued if an interim analysis shows a significant increase in the adverse events presented above compared with a retrospective control.

Adverse Event Criteria and Reporting Procedures

A data safety and monitoring board (DSMB) will be composed of two clinicians knowledgeable in the postoperative care of children with congenital heart disease. The DSMB for this study will include [name], Director of Respiratory Care, and staff Anesthesiologist and Intensivist at Boston Children's Hospital, and [name], a staff Cardiac Anesthesiologist at Boston Children's Hospital. Meetings will be held at the discretion of the DSMB members and study investigators, at least once following enrollment of the first 5 patients. The following complications will be specifically monitored for and reported to the DSMB immediately upon occurrence: accidental extubation or central venous catheter removal thought to be related to the monitoring devices (these are both extremely unlikely given that they are FDA-approved, widely used devices in children).

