Data Management and Statistical Analysis

Data management methods

Upon entry into the study, each patient will be assigned a unique patient identifier which is unique from their medical record number for the purpose of patient tracking. A spreadsheet which links each patient's UPI and BCH medical record number will be

kept in a separate binder, locked in the PI's office. The UPI will be used to identify patients on all study-related materials, including the laptop used to collect data from the GE monitor (which includes all ventilation parameters and SVC measurements), and on the data collection forms. Data from the T3 system will be extracted from SQL T3 database, and stored in a deidentified manner using the same UPI.

Logistic considerations

At the time of study enrollment, baseline characteristics will be collected and recorded on a deidentified form. At the time of first intubation or CVL placement, the pole-mounted GE monitor will be brought to the room by study personnel, and data recording will begin in realtime to the S5 Collect program using an attached laptop (**Figure 6**). The program file will be saved as the patients UPI and will not contain confidential information. Care will be taken to synchronize the time stamps within each of the devices in order to ensure proper alignment of the various data sources.

Each day, a member of the study team will visit the patient's bedside to abstract the relevant information from the medical record, with corroboration from the patient's bedside nurse and treating team. When needed, the patient's cardiac anesthesiologist or perfusionist will be contacted to clarify.

Using a study laptop, all requisite information will be entered into a Microsoft Excel spreadsheet with the desired values listed on the left and each hour listed across the right. Data will be hand-entered into the spreadsheet by a member of the research team, and annotated as necessary to clarify discussions with relevant parties. These data will be double checked by a second member of the study team within 7 days.

Quality control methods

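### The discontinuation rule compares prospectively monitored complications with an undefined retrospective control, and nothing makes event source, definitions or time at risk the same in both groups

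*Combined protocol and SAP*

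**What the plan says.** Under Adverse events, the protocol says of the study infants that "we will monitor vigilantly for complications associated with the standard therapies used in these patients for differences in study patients". It gives ventilator-associated pneumonia, accidental extubation and catheter-associated bloodstream infection as examples, without case definitions.

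Under Logistic considerations, "Each day, a member of the study team will visit the patient's bedside to abstract the relevant information from the medical record". What is abstracted is confirmed with the nurse at the bedside and the treating clinicians. A second team member checks the entries within 7 days.

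Under Parameters for discontinuation of the research, "the research will be discontinued if an interim analysis shows a significant increase in the adverse events presented above compared with a retrospective control". The words "compared with a retrospective control" are all the protocol says about the control. It does not give the period, diagnoses, number of infants, source of events or denominator, and it gives no test, threshold or timing for the interim analysis.

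Under Adverse Event Criteria and Reporting Procedures, the events reported immediately to the DSMB are narrower: "accidental extubation or central venous catheter removal thought to be related to the monitoring devices". The DSMB is to meet at least once after the first 5 patients, but that meeting is not called the interim analysis.

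Specific Aim 1 hypothesises no increased incidence of equipment-related adverse events and names no comparator.

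**The concern.** A between-group difference in complication rates can be read as a device effect only if an event has the same chance of being counted in each group. Here one group is watched prospectively and its chart data are checked the same day with the people at the bedside. The other is looked back on and cannot have that check. Ventilator-associated pneumonia is especially sensitive to the definition used and to how hard one looks.

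A decision to end the study hangs on this comparison, and so would any Aim 1 safety claim that used the same control. If an increase appeared, nobody could separate device harm from closer watching. If none appeared, an era or case-mix difference could be hiding one. This is bias and not imprecision, so enrolling more infants would not remove it.

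**Working it through.** The plan states no rate, control size or threshold for this rule, so there is no figure of its own to reproduce. The calculation below only shows how far unequal recording could matter.

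**Inputs**
- From the protocol: 20 + 20 = 40 infants planned (Study Design), and a DSMB meeting after the first 5.
- Assumed: true event risk p, the same in both groups; control capture s, the share of control events recorded relative to study infants; n2 = 200 controls; one-sided Fisher exact test at 5%; a single look; 20 infants as a possible interim size.

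**Apparent ratio.** With equal true risk, the expected observed ratio is p / (s × p) = 1/s. That is 1/0.8 = 1.25 at 80% capture and 1/0.6 = 1.67 at 60%.

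**False-trigger probability.** Let the study count be X ~ Bin(n1, p) and the recorded control count Y ~ Bin(n2, s × p). The rule triggers when the study proportion is higher and the Fisher p-value is at most 0.05. Summing P(X = x) × P(Y = y) over all triggering pairs gives, for s = 100% / 80% / 60%:

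| Infants | p = 5% | p = 10% | p = 20% |
|---|---|---|---|
| 5 | 2.1 / 2.3 / 2.6% | 1.5 / 3.5 / 6.5% | 2.1 / 4.8 / 6.1% |
| 20 | 2.1 / 3.6 / 6.3% | 2.5 / 5.2 / 10.2% | 3.0 / 7.7 / 17.5% |
| 40 | 2.8 / 5.2 / 9.4% | 3.0 / 7.1 / 16.3% | 3.3 / 11.1 / 30.1% |

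The 40-infant row describes a final comparison. By then enrolment is complete and there is little left to stop.

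**Sensitivity (20 infants, p = 10%).** An upper tail of 2.5% gives 1.3 / 2.9 / 6.1%. With 100 controls at the 5% level, the figures are 2.5 / 4.8 / 8.9%.

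**Very early look.** With 5 infants and p = 10%, the chance of no study event at all is 0.9^5 = 59%, so a spurious increase is often impossible.

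**Does size cure it?** At ten times the full size (400 v 2000, p = 10%, s = 80%), the false-trigger probability is 33%, against 7.1% at 40 v 200.

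**The case against.** The strongest reply is that the documents never say control events are under-recorded. A reader might infer that equal true rates are bound to look like an increase. That does not follow: how control events will be found is not stated, and they could come from the same kind of records.

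A reader might also infer a dedicated bedside search for adverse events. The daily visit is described as chart abstraction with corroboration. Most endpoint data come from the medical record, labs are drawn at the treating team's discretion, and no study-driven cultures or imaging are specified. Accidental extubation, pneumonia and bloodstream infection would normally be charted by the treating team in either group. The difference in ascertainment is therefore narrower than two separate detection systems.

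The direction is open too. An earlier era or a sicker case mix could raise control rates. If the relatedness filter on immediate DSMB reports were carried into the comparison, it would lower the study count with no counterpart in controls. The discontinuation rule's own wording does not apply that filter.

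Finally, the only significance level in the documents, 0.05 two-tailed, belongs to the VO2 comparison, so the test used above is a choice.

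All of this stands, and it limits the claim to a conditional one. It does not supply what is missing: nothing in the plan aligns source, definitions or time at risk. Study follow-up is tied to tube and catheter presence, ending in one account at the later of the two removals. That does not provide device-specific time at risk for either group.

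**Conclusion.** The concern holds in conditional form. As written, the comparison that can end the study is open to detection bias, and the plan has no provision against it. If the control records 60–80% of what study surveillance would find, the false-trigger probability at 20 infants and a 10% true rate is about 5–10%, against 2.5% with equal capture. At 5 infants it is 3.5–6.5%, against 1.5%. Capture, true rate, control size, test and look time are all assumptions; at low rates or very early looks the effect is small.

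The documents do not support saying that a false increase will occur, or that the net bias must run in that direction. They support saying that an observed difference, or its absence, could not be interpreted. This should be corrected before any interim comparison is made.

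**What to change.** For the discontinuation comparison, and for any Aim 1 contrast that uses the same control:

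- Define the control: period, diagnoses and operations, and number of infants.
- Count events in both groups from the same routine records, with the same written case definitions and no device-relatedness filter.
- Compare rates per ventilator-day for tube complications and per catheter-day for line complications, counting only time with the device in place.
- State the test, the threshold and the timing of the interim analysis.
- Report events found only by study surveillance to the DSMB alongside this comparison, so that it can still act on them, and show the comparison with and without them.

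The cost is protocol wording and chart abstraction of device-days in the control. The real downside is that the like-for-like comparison has fewer events and so is less sensitive to true device harm. For that reason the surveillance-only events must stay in front of the DSMB as possible grounds for action in their own right.

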exhibited a pronounced decrease in their measured VO_2 , a pattern which was not present in treated animals which did not experience subsequent hemodynamic instability (**Figure 3**). Having seen this pattern consistently in approximately $n=40$ animal experiments (weight range 2.5-4 kg), we hypothesize that in critically ill patients, VO_2 may decrease below the critical DO_2 and exhibit measureable, even striking, decreases prior to hemodynamic decompensation takes place. If this hypothesis is true, quantification of VO_2 may represent a new 'vital sign' which represents end organ oxygen delivery in critically ill patients. Identification of patients with pathologically supply dependent VO_2 may permit definitive interventions to take place, e.g. initiation of extracorporeal life support, prior to a life-threatening PLOC.

Study Objectives

Specific Aim 1. To demonstrate that oxygen consumption (VO_2) and superior vena cava (SVC) saturations can be safely and precisely measured continuously in newborns undergoing surgery for hypoplastic left heart syndrome (HLHS) or d-transposition of the great arteries with an intact ventricular septum (d-TGA/IVS).

Hypothesis: Measurement of these oxygen-based parameters will not be associated with an increased incidence of equipment-related adverse events (e.g. line displacements, inadvertent extubations) and will lead to precise and reproducible measurements of these important parameters.

Specific Aim 2. To determine whether postoperative loss of circulation (PLOC, defined as cardiac arrest requiring CPR, ECMO cannulation, or causing death) in these patients are associated with a change in oxygen consumption or SVC saturation prior to the event.

Hypothesis: PLOC will be associated with significant decreases in both oxygen consumption and SVC saturations for at least 10 minutes prior to the onset of cardiac arrest.

Specific Aim 3. To determine whether the addition of the oxygen-based measurements to standardly measured parameters (i.e. vital signs, near-infrared spectroscopy

[figure not shown]

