Figure 3. In a proof of concept study, VO_2 monitoring of rabbits (weight ~3 kg) undergoing a 30 minute period of observation, followed by a 15 minute period of asphyxia, then a post-asphyxial recovery. Exemplary VO_2 tracings shown of animals treated (blue line) and untreated (red line) with an intravenous formulation of oxygen which prevented severe hypoxemic-ischemic injury. Animals which suffered severe injury exhibited a significant decrement in VO_2 early during the recovery period, a pattern which worsened prior to post-asphyxial loss of circulation. Animals who experienced treated asphyxial injury had an unchanged VO_2 curve. **A central hypothesis of this study is therefore whether VO_2 may represent a sensitive, real-time, prospective, and non-invasive marker of circulatory failure and inadequate DO_2 in newborns at risk for this life-threatening problem.**

measurements, intermittent measurements of lactate and superior vena cava saturations) add power in predicting which patients will experience PLOC.

Hypothesis: Continuous measurements of VO₂ and SVC saturations will add significantly to our ability to predict which patients will undergo PLOC.

Study Design

We will prospectively and continuously measure VO₂ and SVC saturations in newborns undergoing stage I palliation (S1P) or hybrid palliation (HP) for HLHS (n=20) or arterial switch operation (ASO) for d-TGA/IVS (n=20), beginning at the time of first preoperative intubation and ending at the time of the first postoperative extubation. Newborns will be followed for the occurrence of PLOC as the primary endpoint. A study schematic is attached as **Appendix 1**.

Study Population

Inclusion criteria.

1. Patient from birth to 6 months of age
2. HLHS AND no prior operations AND planned S1P or HP
OR
d-TGA/IVS AND planned ASO
3. Written parental informed consent

Exclusion criteria.

1. Weight < 2 kg
2. Disease specific
 - A. HLHS patients: Infants whose surgical plan includes a neonatal biventricular repair will be excluded.
 - B. d-TGA/IVS patients: Newborns with any additional cardiac defect other than an atrial septal defect will be excluded.
3. Patients on ECMO preoperatively
4. Clinically significant tracheo-esophageal fistula or known preoperative air leak

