Quality in the data collected by the oxygen consumption monitor will be ensured by a self-test at startup according to the manufacturer's instructions. Further, anesthesiologist and respiratory care staff will be instructed to monitor for the degree of air leak from the respiratory system by calculating the difference between inspiratory and expiratory measured tidal volumes. If the airleak exceeds this value, air may be added to the tracheal tube cuff. We have shown that when this difference is <15%, VO_2 data are accurately measured in newborns.²⁴ Further, an absence of end-tidal CO_2 data will be used as a signal of an endotracheal tube disconnection and possible suctioning event. VO_2 measurements are known to be unstable for several minutes following suctioning²⁸, so we will exclude VO_2 data for 10 minutes following any ETT disconnect from analyses.

Figure 6. The oxygen-based monitoring and data collection systems utilized for this study are attached to a rolling pole which can be placed anywhere around the patient and easily moved for convenience and safety.

Data within the SVC monitoring probe will be ensured by an in vitro calibration prior to probe insertion. When ever the treating team sends a venous blood gas from the central venous line, the co-oximetry value will be entered into the machine and used to recalibrate the probe in real-time.

Quality in the transfer of data from the medical record to the spreadsheet will be ensured by an independent review of the primary data by a second member of the study team. Furthermore, when possible, the fields for data entry will contain 'Data Validation' functions (i.e. value will turn red if outside expected limits, and hard stops will be inserted for physiologically impossible values). Additionally, drop down lists will be utilized when possible to minimize data entry errors.

Data Analysis Plan

Patients will be divided into patients who do and do not experience PLOC. All variables will be normalized to hours prior to bypass, bypass time and hours post-bypass time, such that all data for a specific post-bypass time will be aligned between patients. All weight-dependent variables will be normalized to preoperative body weight. Using GraphPad Prism, each variable will be entered into a different column for analysis.

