Simple analyses (e.g. mean, standard deviation, tests for normality) will be completed within GraphPad. With regards to the primary endpoint, VO₂ measurements will be analyzed for 120 minutes prior to a PLOC event in cases, and a randomly selected 120 minute period in controls. Values will be compared between cases and controls using generalized estimating equations (GEEs) to account for the correlation of multiple measurements within the same patient and to compare means between cases and controls. A post-hoc broken stick analysis will be used to determine the time prior to the event at which the VO₂ changed in each patient experiencing an event. Data for HLHS and dTGA patients will be pooled together.

More complex analyses will be completed by a collaborating company called Etiometry (including [name] and [name], co-investigators on this study), with whom the PI and others within the CICU have an established relationship. Deidentified information will be sent to the company, who will complete further analyses.

Power Calculations and Sample Size

The measured oxygen consumption in neonates following S1P has been described as 86 ± 16 mL/min/m^{2.22}. A sample size that includes 3 cardiac arrest events would allow us to detect a true decrease of 53 mL/min/m² in oxygen consumption with 90% power and a significance level of 0.05 (two tailed). Based on the significant change in VO₂ noted in the animal studies preceding cardiac arrest, we do not feel that this number is an unreasonable number. In order to collect 3 patients meeting the endpoint, we predict that we will require 20 patients undergoing S1P.

Risks and Discomforts

Because this is a prospective, observational study which we do not expect to change the standard of care, the risks associated with this study are really those of the standard

of care. The VO_2 measurements will be taken using an FDA-approved device which samples gas from the side of the tracheal tube of each patient. In reality, the adapter used by the study monitor is smaller and lighter than than used in our current capnographs, so the risk of accidental endotracheal tube removal should be the same or lower.

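### VO2 accuracy is stated only for air leak below 15%, but no analysis rule removes VO2 recorded during a larger leak (minor; cheap to fix)

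*Combined protocol and SAP*

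**What the plan says.** Under Quality control methods, anesthesia and respiratory care staff are to watch for leak by comparing inspired and expired tidal volumes. The accuracy statement is: "We have shown that when this difference is <15%, VO_2 data are accurately measured in newborns". The response to a larger leak is: "If the airleak exceeds this value, air may be added to the tracheal tube cuff". I read the value referred to there as the 15% given in the next sentence. The section has one data exclusion for VO2, signalled by missing end-tidal CO2: "we will exclude VO_2 data for 10 minutes following any ETT disconnect from analyses".

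The Data Analysis Plan sets no leak condition on either use of VO2. The main comparison is set out as follows: "VO₂ measurements will be analyzed for 120 minutes prior to a PLOC event in cases, and a randomly selected 120 minute period in controls", with GEE used to compare the groups. For each patient with an event, "A post-hoc broken stick analysis will be used to determine the time prior to the event at which the VO₂ changed".

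Other safeguards bear on leak:

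- The exclusion criteria remove infants with "Clinically significant tracheo-esophageal fistula or known preoperative air leak".
- The Appendix 1 schematic shows a tube leak check at first intubation.
- The VO2 monitoring section keeps tidal volume on the clinicians' display for the whole study. VO2 itself is recorded but not shown.

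Study Design has measurement "beginning at the time of first preoperative intubation and ending at the time of the first postoperative extubation". Inspiratory and expiratory tidal volumes are among the ventilatory parameters stored every second.

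**The concern.** The authors saw that some VO2 readings are unreliable and wrote a rule to drop those that follow a disconnect. They did not write the matching rule for their other validity condition, the 15% leak limit. A leak with end-tidal CO2 still present does not trigger the disconnect rule, and adding air to the cuff does nothing to VO2 already stored.

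The study plans on 3 events, so each case window carries a third of the case mean. The broken-stick analysis is more exposed, because it is fitted in one case at a time and Aim 2 looks for a fall lasting "for at least 10 minutes prior to the onset of cardiac arrest". A leak of similar length inside the window could be taken for the signal, or could hide it. If leak filtering is left until VO2 and outcome are known, it also becomes an avoidable analytic choice.

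**Working it through.** **Step 1. Match each leak provision to the analysis windows.**

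| Provision | When it acts | Removes recorded VO2? |
|---|---|---|
| Exclusion for fistula or known leak | Before surgery | No |
| Leak check in schematic | First intubation | No |
| Staff monitoring, optional cuff air | During the study | No |
| 10-minute exclusion | After a disconnect | Yes, but not triggered by leak |
| Data-entry validation | Spreadsheet transfer | No; range checks on entry fields |

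No row removes or flags VO2 recorded at a leak of 15% or more.

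**Step 2. The plan's own figure.** Power Calculations and Sample Size gives mean 86, SD 16, 3 events, and 90% power for a fall of 53 mL/min/m² at two-sided 0.05. The comparator size and test are not stated. A two-sample t-test gives 85.3% for 3 against 3 and 99.9% for 3 against 17, so the 90% is not reproduced. That is a separate matter, and this point does not depend on it.

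**Step 3. Shift in the case mean (illustration).** Assume VO2 is wrong by a fraction e for m of 120 minutes in one of three case windows:

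shift = 86 × e × (m/120) / 3

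- e = 0.15, m = 60: 86 × 0.15 × 0.5 / 3 = 2.15 (4% of 53)
- e = 0.15, m = 120: 86 × 0.15 / 3 = 4.3 (8% of 53)
- e = 0.30, m = 30: 86 × 0.30 × 0.25 / 3 = 2.15 (4% of 53)
- e = 0.30, m = 120: 86 × 0.30 / 3 = 8.6 (16% of 53)

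**Step 4. False-positive rate (simulation).** Assumptions: 3 cases and 40 − 3 = 37 controls (both diagnoses pooled, as planned), normal window means, SD 16, no true difference, and a two-sided t-test at 0.05 standing in for the GEE. Ranges cover errors in either direction.

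| Assumed error | Windows affected | False positives |
|---|---|---|
| 10-15%, 30 min | One case, no controls | about 5% |
| 10-15%, 60 min | One case, no controls | about 5-6% |
| 10-15%, 120 min | One case, no controls | about 5-8% |
| 30%, 30 min | One case, no controls | about 5-6% |
| 30%, 30 min | 20% of cases, 10% of controls | about 5% |
| 30%, 120 min | 20% of cases, 10% of controls | about 7-8% |
| 30%, 30 or 120 min | 20% of both groups | about 5% |
| 30%, 120 min | One case, no controls | about 12-15% |

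Only the last row, a large error lasting the whole window in a case alone, moves the rate well away from 5%. In this model, power at a fall of 53 stays at 99% or more when one case window carries an error of up to 30%.

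**Step 5. Broken stick.** The argument is qualitative. The method places a breakpoint in one patient's series wherever the level or slope changes. As described, it has no term for leak, so an artefact and a true fall look the same to it. No control group averages this out.

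**The case against.** The strongest reply has four parts.

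- **Leak is watched.** Staff are told to monitor it, nothing confines this to first intubation, and tidal volume stays on display. A large leak lasting two hours is therefore less likely. This stands, and it is why the point is minor. But correction is optional, no frequency or log is stated, and staff cannot see VO2.
- **Nothing shows that VO2 is wrong above 15%.** This also stands. A reader might infer that such data are known to be invalid, or that the plan intends to keep them. The documents say neither. They state accuracy below 15% and are silent above it.
- **The primary comparison hardly moves.** This is largely right. A reader might infer that the primary test is seriously compromised. That needs a large, sustained error confined to cases, and no document gives evidence of one.
- **Nothing is lost, and a filter has its own risk.** Tidal volumes are stored, so leak can be derived later. A rule applied second by second could discard data on single breaths, and lost minutes before an arrest could themselves bias three cases. This stands as a condition on the fix. It does not remove the case for choosing the rule before VO2 and outcome are seen.

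The broken-stick analysis is also labelled post hoc and is not the primary test, which limits what rests on it.

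**Conclusion.** The gap is real and minor. The stated exclusion rule lets VO2 from outside the range with stated accuracy into both analyses, and ongoing bedside monitoring reduces that risk without closing it. The size and direction of any error cannot be known from the documents, which give neither leak frequency nor the behaviour of VO2 above 15%.

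Under the assumptions in the working, the primary test keeps a false-positive rate of about 5-8%, apart from the large, sustained, case-only scenario. The main exposure is the breakpoint in each case, where one leak artefact among about 3 cases could be reported as the time VO2 changed. The documents do not support a numerical estimate of how far a leak would move a breakpoint: a continuous hinge fitted to any late step places the break in the same spot, whether the step is artefact or a true fall.

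**What to change.** Add one validity rule to the Data Analysis Plan:

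1. Compute leak = (inspiratory − expiratory tidal volume) / inspiratory tidal volume from the recorded data, averaged over a fixed short interval, for example 1 minute.
2. Exclude VO2 from intervals with leak of 15% or more. Apply this identically to cases and controls, without sight of VO2, in both the GEE comparison and the broken-stick analysis.
3. Report valid minutes per 120-minute window.
4. Repeat the primary analysis unfiltered as a sensitivity analysis.

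This needs one derived variable and a few lines of text, with no new measurement and no change to bedside care. The downside is some lost VO2 minutes, possibly in the few cases. Averaging prevents exclusions triggered by single breaths, and the unfiltered analysis shows whether the lost minutes matter to the primary result.
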